### **3.2.3 Rationale for Endpoints**

#### **3.2.3.1 Efficacy Endpoints**

The primary efficacy objective of this trial is to determine Progression Free Survival (PFS) from the date of ASCT, with day 0 defined as date of stem cell infusion (if tandem transplant the 2nd of 2 transplants will be used) until the date of progression, defined as the date at which the patient starts the next line of therapy or the date of death. The Overall Survival (OS) will also be calculated from the date of ASCT as previously defined until the date of death.

The secondary efficacy objective of this trial is to evaluate the anti-tumor activity of pembrolizumab (MK-3475), lenalidomide and dexamethasone in subjects with high-risk MM post-ASCT. This will be complete response (CR) + stringent complete response (sCR) + very good partial response (VGPR) rate and objective response rate (ORR) as assessed by the investigator per International Myeloma Working Group (IMWG) uniform response criteria for MM[57].

Immunotherapeutic agents such as pembrolizumab (MK-3475), lenalidomide and dexamethasone may produce anti-tumor effects by potentiating endogenous cancer-specific immune responses, which may be functionally anergic. The response patterns seen with such an approach may extend beyond the typical time course of responses seen with cytotoxic agents, and can manifest a clinical response after an initial increase in tumor burden or even the appearance of new lesions. Standard response assessment criteria may not provide a comprehensive response assessment of immunotherapeutic agents such as pembrolizumab (MK-3475), lenalidomide and dexamethasone. Disease response assessment will be performed every 21-day treatment cycles. PD must be confirmed prior to discontinuation from study.

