#### 4.1.2 Subject Inclusion Criteria

In order to be eligible for participation in this trial, the subject must:

1. Be willing and able to provide written informed consent/assent for the trial.
2. Be  $\geq 18$  years of age on day of signing informed consent.
3. Has a confirmed diagnosis of MM based on standard criteria. (See Appendix 2 for MM Diagnostic Criteria.)

4. Is between 60 and 180 days from peripheral blood autologous stem cell transplant.

5. At diagnosis, had MM with measurable disease, defined as:

- A monoclonal immunoglobulin spike on serum electrophoresis of at least 0.5 g/dL and/or
- Urine monoclonal levels of at least 200 mg/24 hours
- For subjects without measurable serum and urine M-protein levels, an abnormal free light chain (FLC) ratio (normal value 0.26 – 1.65) with involved FLC  $\geq 10$  mg/dL
- Radiographic evidence of disease for those without measurable M-spike or free light chains.

6. Has high-risk MM, which must be present at the time of diagnosis, and defined by:

- a. International Staging System (ISS) stage 3 (See Appendix 3 for ISS Staging), and/or
- b. Deletion 13q by cytogenetics, and/or
- c. 1q amplification, 1p deletion, p53 deletions (17p deletions), t(4;14), t(14;16), t(14;20), hypodiploidy, and/or
- d. High-risk gene expression profile (GEP) scores

7. Be able to provide a newly obtained bone marrow aspirate/biopsy material for biomarker analysis and disease assessment.

8. Have a performance status of  $\leq 2$  on the ECOG Performance Scale (See Appendix 4).

9. Demonstrate adequate organ function as defined in Table 1, all screening labs should be performed within 28 days of treatment initiation.

Table 1 Adequate Organ Function Laboratory Values

System	Laboratory Value
Hematological	
Absolute neutrophil count (ANC)	$\geq 1,000$ /mcL
Platelets	$\geq 75,000$ / mcL
Hemoglobin	$\geq 8$ g/dL or $\geq 5.6$ mmol/L without transfusion or EPO dependency (within 7 days of assessment)
Renal	
Serum creatinine OR Measured or calculated a creatinine clearance (GFR can also be used in place of creatinine or CrCl)	$\leq 1.5$ X upper limit of normal (ULN) OR $\geq 60$ mL/min for subject with creatinine levels $> 1.5$ X institutional ULN
Hepatic	

Serum total bilirubin	
	$\leq 1.5 \times \text{ULN}$ OR
	Direct bilirubin $\leq \text{ULN}$ for subjects with total bilirubin levels $> 1.5 \text{ ULN}$
AST (SGOT) and ALT (SGPT)	

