##### **7.1.6.1 Efficacy Endpoints**

Key efficacy endpoints for the trial include the following as assessed by IMWG:

- PFS: defined as the time from Day 0 of ASCT to progressive disease (PD) or death, whichever occurs earlier, per IMWG criteria by investigator assessment. Subjects without documented PD/death will be censored at the last disease assessment date.
- Complete response, stringent complete response, and very good partial response rate (CR + sCR + VGPR) rate using IMWG criteria. Response rates will be determined with the following baselines 1) Prior to ASCT 2) Cycle 1 day 1 of study drug or screening visit, whichever is higher.
- ORR: Defined as the proportion of subjects who have achieved sCR, CR, VGPR or PR according to the IMWG criteria by investigator assessment. Subjects with missing outcome on objective response will be considered non-responders. Response rates will be determined with the following baselines 1) Prior to ASCT 2) Cycle 1 day 1 of study drug or screening visit, whichever is higher.
- DOR: defined as the time interval between the date of first response (sCR, CR, VGPR, PR) and the date of first documented disease progression.
- TTP: defined as the time from 1) Day 0 ASCT and 2) Date of enrollment to progressive disease (PD) per IMWG criteria by investigator assessment. Subjects without documented PD or death will be censored at the last disease assessment date, and subjects who died without documented PD will be censored at the time of death.

- OS: defined as the time from Day 0 ASCT to death from any cause.

In addition, overall survival (OS) and change from baseline in bone marrow/aspirate PD-L1 expression, T-cell subsets, and cytokine analysis will be evaluated.

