## 11.5 Multiple Myeloma Disease Response Criteria

Durie et al. International uniform response criteria for multiple myeloma. Leukemia. 2006; 20:1467-1473.

Criteria for multiple myeloma disease assessment:

**Table 5** International Myeloma Working Group uniform response criteria: CR and other response categories

Response subcategory	Response criteria a
sCR	CR as defined below plus Normal FLC ratio and Absence of clonal cells in bone marrow b by immunohistochemistry or immunofluorescence c
CR	Negative immunofixation on the serum and urine and Disappearance of any soft tissue plasmacytomas and ≤5% plasma cells in bone marrow b
VGPR	Serum and urine M-protein detectable by immunofixation but not on electrophoresis or 90% or greater reduction in serum M-protein plus urine M-protein level <100 mg per 24 h
PR	≥50% reduction of serum M-protein and reduction in 24-h urinary M-protein by ≥90% or to <200 mg per 24 h If the serum and urine M-protein are unmeasurable, d a ≥50% decrease in the difference between involved and uninvolved FLC levels is required in place of the M-protein criteria. If serum and urine M-protein are unmeasurable, and serum free light assay is also unmeasurable, ≥50% reduction in plasma cells is required in place of M-protein, provided baseline bone marrow plasma cell percentage was ≥30% In addition to the above listed criteria, if present at baseline, a ≥50% reduction in the size of soft tissue plasmacytomas is also required
SD (not recommended for use as an indicator of response; stability of disease is best described by providing the time to progression estimates)	Not meeting criteria for CR, VGPR, PR or progressive disease

Abbreviations: CR, complete response; FLC, free light chain; PR, partial response; SD, stable disease; sCR, stringent complete response; VGPR, very good partial response.

aAll response categories require two consecutive assessments made at anytime before the institution of any new therapy; all categories also require no known evidence of progressive or new bone lesions if radiographic studies were performed. Radiographic studies are not required to satisfy these response requirements.

bConfirmation with repeat bone marrow biopsy not needed.

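### The Cycle 1 Day 1 response rates can count responses carried in from the transplant, because sCR, CR and one branch of VGPR are absolute states and nothing requires them to be new

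*Combined protocol and SAP*

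**What the plan says.** Section 3.2.3.1 gives the secondary efficacy aim as "to evaluate the anti-tumor activity of pembrolizumab (MK-3475), lenalidomide and dexamethasone in subjects with high-risk MM post-ASCT", and names the sCR+CR+VGPR rate and ORR as its measures. Section 7.1.6.1 sets two baselines for each: "Response rates will be determined with the following baselines 1) Prior to ASCT 2) Cycle 1 day 1 of study drug" or the screening visit, taking the higher of those two pre-dose values.

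Appendix 11.5 supplies the categories:

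- CR: "Negative immunofixation on the serum and urine and Disappearance of any soft tissue plasmacytomas", with a ceiling of 5% on marrow plasma cells.
- sCR: "CR as defined below plus Normal FLC ratio and Absence of clonal cells in bone marrow".
- VGPR: "Serum and urine M-protein detectable by immunofixation but not on electrophoresis or 90% or greater reduction in serum M-protein plus urine M-protein level" under 100 mg per 24 h.
- PR: "≥50% reduction of serum M-protein and reduction in 24-h urinary M-protein by ≥90% or to <200 mg per 24 h".

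A footnote there requires two consecutive assessments for every response category.

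On entry, Section 4.1.2 asks for measurable disease in the past tense only: "At diagnosis, had MM with measurable disease, defined as". It admits patients 60 to 180 days after transplant. Exclusion 7 in Section 4.1.3 removes patients with progression at screening; no criterion removes those already in sCR, CR or VGPR. The full analysis set (Section 7.1.7.1) is defined by dosing plus either a post-baseline assessment or discontinuation for progression or a drug-related adverse event. Section 7.1.8.1 plans an exact binomial p-value against a historical control, with a 90% interval, and states no control rate.

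**The concern.** A response endpoint meant to measure the regimen has to separate what happened after the first study dose from what the transplant had already achieved. The pre-transplant baseline cannot do so by construction. The Cycle 1 Day 1 baseline looks like the remedy, but a baseline matters only for criteria expressed as a change. A patient who enters with negative immunofixation and a clear marrow, and stays so, satisfies CR whatever baseline is named.

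Two things are at stake. The reported rate may be read as activity of the regimen when part of it was present at entry. The planned test against a historical control may also succeed for that reason alone. In the other direction, patients with too little M-protein to show a relative reduction stay in the denominator, which pulls the PR part of ORR down.

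**Working it through.** The documents give no expected response rate, control rate or power for these endpoints, so there is no planned figure to reproduce. The check first sorts the criteria, then shows the size under stated assumptions.

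**Which categories depend on baseline (Appendix 11.5)**

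| Category | Judged as | Carried in under the Cycle 1 Day 1 baseline? |
|---|---|---|
| sCR, CR | state | yes, if maintained over two assessments |
| VGPR, electrophoresis-negative branch | state | yes, if maintained over two assessments |
| VGPR, 90%-reduction branch | change | no |
| PR | change | no |

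The two change-based rows carry one small qualification. Because the higher of the screening and Cycle 1 Day 1 values is used, a fall between those two pre-dose visits would count as reduction.

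**Is a carried-in state screened out elsewhere?** Eligibility does not exclude it (Sections 4.1.2 and 4.1.3). The full analysis set does not require measurable disease at entry (7.1.7.1). The two-assessment rule confirms a response but does not require it to be new. No section requires an upgrade from the entry category.

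**Size.** Let f be the share entering in sCR, CR or electrophoresis-negative VGPR, and c the share of the remaining patients who newly reach VGPR or better. If carried-in patients keep their category until it is confirmed:

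reported sCR+CR+VGPR rate = f + (1 − f)c.

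Neither f nor c is in the documents; f is varied from 20% to 60%. N = 43 is the planned evaluable number (Section 7.1.10).

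*No drug effect (c = 0).* The reported rate is f:

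- f = 20%: 0.20 × 43 = 8.6, about 9/43, exact 90% interval 11% to 34%
- f = 40%: 17.2, about 17/43, 27% to 53%
- f = 60%: 25.8, about 26/43, 47% to 73%

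*Some effect.* With f = 50% and c = 20%, the rate is 0.50 + 0.50 × 0.20 = 0.60. New responses are 0.10 of all patients; the other 0.50 was present at entry.

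*Test against a historical control.* Let h be the control rate (assumed) and k the smallest count with P(X ≥ k | 43, h) ≤ 0.05. The one-sided 0.05 level is also assumed for this endpoint; the plan states it for PFS. The table gives P(X ≥ k | 43, f), the chance that an inactive regimen passes:

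| h | k | f = 20% | 30% | 40% | 50% | 60% |
|---|---|---|---|---|---|---|
| 10% | 9 | 0.50 | 0.93 | >0.99 | >0.99 | >0.99 |
| 20% | 14 | 0.04 | 0.41 | 0.88 | 0.99 | >0.99 |
| 30% | 19 | <0.01 | 0.03 | 0.34 | 0.82 | 0.99 |
| 40% | 24 | <0.01 | <0.01 | 0.03 | 0.27 | 0.76 |

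Where h equals f the test keeps its level (0.04, 0.03 and 0.03 at 20%, 30% and 40%). The false positives arise where f exceeds the control rate, so the missing control rate matters as much as the missing entry mix.

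**The case against.** The strongest reply is that the plan is silent rather than wrong. It provides a post-transplant baseline, the flow chart records the response category at screening and Cycle 1 Day 1, and an analyst could read ORR as counting only responses achieved afterwards. These are secondary endpoints without a power calculation, and the decision to continue rests on 12-month PFS. All of that is true. But Section 7.0 says no separate SAP will be issued, so this text is the only pre-specification. Applied literally, it counts a maintained CR, and in an open-label trial the alternative reading would be chosen with the data in view.

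A reader might also infer more than the documents support:

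- **That a patient in CR at entry is a responder at the first on-study assessment.** The two-assessment rule prevents this.
- **That everyone in VGPR or better at entry carries over under the Cycle 1 Day 1 baseline.** Patients in VGPR only through the 90%-reduction branch, with M-protein still visible on electrophoresis, do not.
- **That the pre-transplant baseline is itself an error.** Section 1.1 frames the primary objective as transplant followed by consolidation, and PFS runs from the transplant date. A pre-transplant response rate is a legitimate description of that whole strategy; it just cannot serve the aim in Section 3.2.3.1.
- **That a 60% reported rate should be set against a 20% conversion rate.** Those have different denominators. On all patients, the comparison is 60% against 10%.

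**Conclusion.** The point stands in a limited form. The pre-transplant rate describes the combined strategy. The Cycle 1 Day 1 rate does not fully isolate the regimen, because absolute-state responses present at entry qualify once maintained over two assessments. The sCR+CR+VGPR rate is inflated by up to about f with an inactive regimen. ORR is inflated through the same absolute-state component only, and is pulled down by patients unable to show a relative reduction, so its net bias has no fixed sign.

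It does not follow from the definitions alone that an inactive regimen would show a high response rate. That depends on f, which the documents do not give, and on carried-in patients keeping their category. The test probabilities (0.41 at f = 30% and 0.88 at f = 40%, for a 20% control) rest also on the assumed control rate, N = 43 and a one-sided 0.05 level. The primary PFS endpoint and its two-stage rule are not affected. The text should be amended, but the design need not change.

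**What to change.** In Section 7.1.6.1:

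1. Define regimen response as a confirmed improvement on the Cycle 1 Day 1 category. Report the proportion reaching VGPR or better among patients below VGPR at Cycle 1 Day 1, and ORR among patients with measurable disease at that point.
2. Cross-tabulate Cycle 1 Day 1 category by best confirmed on-study category for all treated patients, so that maintained and new responses are both visible.
3. Keep the rate from the pre-transplant baseline, labelled as a description of transplant plus consolidation.
4. Start duration of response from the same definition, since the present start date is not limited to after the first dose.

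In Section 7.1.8.1, state the historical control rate and its source, and run the exact test only where that rate matches the chosen baseline and population. Otherwise report the estimate and interval without a p-value.

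No new visits or samples are needed, as response and myeloma laboratory data are already collected at screening and Cycle 1 Day 1. The cost is a smaller denominator and a wider interval. For example, if 40% of 43 patients entered already in the category, about 43 − 17 = 26 would remain for the VGPR-or-better rate.

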#### 4.1.3 Subject Exclusion Criteria

The subject must be excluded from participating in the trial if the subject:

1. Is currently participating and receiving study therapy or has participated in a study of an investigational agent and received study therapy or used an investigational device within 4 weeks of the first dose of treatment.

Pembrolizumab (MK-3475), [name], HUMC

2. Has a diagnosis of immunodeficiency or is receiving systemic steroid therapy or any other form of immunosuppressive therapy within 7 days prior to the first dose of trial treatment. The use of physiologic doses of corticosteroids may be used at the investigator's discretion.
3. Has received an allogeneic stem cell transplant.
4. Has received any myeloma-directed therapy after ASCT.
5. Has a known history of active TB (Bacillus Tuberculosis)
6. Hypersensitivity to pembrolizumab or any of its excipients.
7. Progressive disease from autologous transplantation at the time of screening. See Appendix 11.5 for criteria
8. Has known active central nervous system (CNS) metastases and/or carcinomatous meningitis. Subjects with previously treated brain metastases may participate provided they are stable (without evidence of progression by imaging for at least four weeks prior to the first dose of trial treatment and any neurologic symptoms have returned to baseline), have no evidence of new or enlarging brain metastases, and are not using steroids for at least 7 days prior to trial treatment. This exception does not include carcinomatous meningitis which is excluded regardless of clinical stability.
9. Has active autoimmune disease that has required systemic treatment in the past 2 years (i.e. with use of disease modifying agents, corticosteroids or immunosuppressive drugs). Replacement therapy (eg., thyroxine, insulin, or physiologic corticosteroid replacement therapy for adrenal or pituitary insufficiency, etc.) is not considered a form of systemic treatment.
10. Has a history of (non-infectious) pneumonitis that required steroids or current pneumonitis.
11. Has an active infection requiring intravenous systemic therapy.
12. Has a history or current evidence of any condition, therapy, or laboratory abnormality that might confound the results of the trial, interfere with the subject's participation for the full duration of the trial, or is not in the best interest of the subject to participate, in the opinion of the treating investigator.

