Quantitative serum immunoglobulins 	X	X		X		X		X		X	
Serum protein electrophoresis and serum immunofixation 	X	X		X		X		X		X	
Serum free light chain analysis 	X	X		X		X		X		X	
24 hour urine protein electrophoresis and urine immunofixation 	X	X		X		X		X		X	
M-protein quantitation (urine and/or serum) 	X	X		X		X		X		X	
Beta-2 microglobulin 	X	X		X		X		X		X	
Bone marrow aspiration and biopsy 	X							X			
Trial Period:	Treatment Cycles						End of Treatment	Post-treatment			
		Cycle = 21 Days									
Treatment Cycle/Title:	Screening (Visit 1)	Cycle 1	Cycle 2	Cycle 3 and 4	At the completion of cycle 4	Post-Treatment Safety Follow-up	Follow-up Visits 	Survival Follow-up 			

Cycle Day					1	15				30 days post completion of cycle 4	Every 12 weeks post completion	
	1	8	15		1	15			Cycle 4	of	post Discon	Every 12 weeks
Bone marrow morphology, IHC, cytogenetics by standard karyotyping, FISH panel, and minimal residual disease (MRD) analysis 		X 17, 19			X 17		X 17		X			
Correlative Studies – bone marrow and peripheral blood collection, stool samples 	X 6	X 6			X		X		X			

1. In general, assessments/procedures are to be performed on Day 1 and prior to the first dose of treatment for each cycle unless otherwise specified. Treatment cycles are 21 days. Unless otherwise noted, procedures should be on Day 1 of each Cycle.
2. Procedures outlined for visit, 30-day Safety-Follow-up and Survival Follow-up should be performed for subjects who complete the study or progress.
3. Subjects who discontinue trial treatment for a reason other than disease progression will move into the Follow-Up Phase and should be assessed every 12 weeks (84 ± 7 days) to monitor disease status. Every effort should be made to collect information regarding disease status
4. In general, the window for each visit is ± 3 days unless otherwise noted.
5. Record all medications taken from 28 days prior to cycle 1 day 1 to the 30 day post completion of cycle 4 visit.
6. For correlative studies, collection will be at screening or cycle 1 day 1, then every day 1 of each cycle, and at completion of cycle 4 and to confirm response.

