7. After documented disease progression or the start of new antineoplastic therapy, each subject will be followed by telephone for overall survival until death, withdrawal consent or the end of the trial, whichever occurs first.
8. AEs and laboratory safety measurements will be graded per NCI CTCAE version 4.03. All AEs, whether gradable by CTCAE or not, will also be evaluated for seriousness. AEs will be evaluated every two weeks, on Days 1 and 15 of each 21-day cycle.
9. Record all AEs occurring within 30 days after the last dose of study drug. Report all SAEs (related and unrelated to trial treatment) and ECIs occurring up until 90 days after the last dose of trial treatment or the start of new anti-cancer treatment, whichever comes first. Afterwards, report only SAEs and ECIs that are related to trial treatment.
10. Directed PE performed to collect any new/clinically significant abnormalities (i.e. ECI/AE).
11. Vital signs to include temperature, pulse, respiratory rate, weight and blood pressure. Height will be measured at screening only.
12. Skeletal survey should include a chest (PA or AP; lateral), skull (lateral), upper extremities (shoulder to elbow), lower extremities (hip to knee; AP), pelvis (AP), cervical/thoracic/lumbar spine (AP and lateral). For suspected progression to bone disease bidimensional measurement of the target lytic lesions must be performed. MRI/CT/PET (MRI for subjects with bone disease and CT/PET for plasmacytomas) is required when clinically indicated for subjects with bony disease and should just include the bony lesions. Subjects with measurable plasmacytomas at baseline should have imaging performed every 12 weeks.
13. Disease response assessment is based upon the multiple myeloma response criteria (See Appendix 5 ). Myeloma lab assessments should be performed every 3 weeks, that is, on Day 1 of every 21-day treatment cycle. Disease assessments should occur at Day 1 of each 21-day treatment cycle (+/- 7 days) throughout the course of the trial.

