#### **6.1.2.10 Initial Disease Assessment**

Initial disease assessments must be performed within 28 days prior to the first dose of trial treatment (See 5.0 – Trial Flow Charts).

Bone marrow aspirates/biopsies performed as part of standard of care prior to signing informed consent may be used for screening if performed within 28 days of Day 1.

Myeloma laboratory disease assessments should be performed within 28 days prior to the first dose of trial treatment (See 5.0 – Trial Flow Charts).

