cPresence/absence of clonal cells is based upon the  $k/\lambda$  ratio. An abnormal  $k/\lambda$  ratio by immunohistochemistry and/or immunofluorescence requires a minimum of 100 plasma cells for analysis. An abnormal ratio reflecting presence of an abnormal clone is  $k/\lambda$  of >4:1 or <1:2.

dRefer to Table 4 for definitions of measurable disease.

**Table 6** International Myeloma Working Group uniform response criteria: disease progression and relapse

Relapse subcategory	Relapse criteria
Progressive disease a To be used for calculation of time to progression and progression-free survival end points for all patients including those in CR (includes primary progressive disease and disease progression on or off therapy)	Progressive Disease: requires any one or more of the following: Increase of ≥25% from baseline in Serum M-component and/or (the absolute increase must be ≥0.5 g/dl) b Urine M-component and/or (the absolute increase must be ≥200 mg/24 h) Only in patients without measurable serum and urine M-protein levels: the difference between involved and uninvolved FLC levels. The absolute increase must be >10 mg/dl. Bone marrow plasma cell percentage: the absolute % must be ≥10% c Definite development of new bone lesions or soft tissue plasmacytomas or definite increase in the size of existing bone lesions or soft tissue plasmacytomas Development of hypercalcemia (corrected serum calcium >11.5 mg/dl or 2.65 mmol/l) that can be attributed solely to the plasma cell proliferative disorder
Clinical relapse d	Clinical relapse requires one or more of: Direct indicators of increasing disease and/or end organ dysfunction (CRAB features) b It is not used in calculation of time to progression or progression-free survival but is listed here as something that can be reported optionally or for use in clinical practice 1. Development of new soft tissue plasmacytomas or bone lesions 2. Definite increase in the size of existing plasmacytomas or bone lesions. A definite increase is defined as a 50% (and at least 1 cm) increase as measured serially by the sum of the products of the cross-diameters of the measurable lesion 3. Hypercalcemia (>11.5 mg/dl) [2.65 mmol/l] 4. Decrease in hemoglobin of ≥2 g/dl [1.25 mmol/l] (see Table 3 for further details) 5. Rise in serum creatinine by 2 mg/dl or more [177 μmol/l or more]

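### Taking the higher of screening and Cycle 1 Day 1 as the on-study response baseline credits any pre-dose fall to the regimen, mainly through PR within ORR

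*Combined protocol and SAP*

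**What the plan says.** Section 7.1.6.1 gives two baselines, in the same words, for the CR + sCR + VGPR rate and for ORR. The text begins "Response rates will be determined with the following baselines 1) Prior to ASCT", and the second baseline is "Cycle 1 day 1 of study drug or screening visit, whichever is higher". No reason is given for preferring the higher value, and neither baseline is named as primary. The PFS, TTP, DOR and OS bullets do not contain this sentence.

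The timing of the two readings is set elsewhere:

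- **Screening** (6.1.2.10): "Myeloma laboratory disease assessments should be performed within 28 days prior to the first dose of trial treatment".
- **Cycle 1 Day 1** (5.1, footnote 1): in general, "assessments/procedures are to be performed on Day 1 and prior to the first dose of treatment for each cycle unless otherwise specified".
- **On treatment** (5.1, footnote 13): "Myeloma lab assessments should be performed every 3 weeks, that is, on Day 1 of every 21-day treatment cycle".

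Entry is tied to the transplant. Inclusion criterion 4 reads "Is between 60 and 180 days from peripheral blood autologous stem cell transplant", and exclusion criterion 4 is "Has received any myeloma-directed therapy after ASCT". Exclusion criterion 7 removes patients who are progressing at screening.

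Appendix 11.5 defines PR by a fall of at least 50% in serum M-protein, with a companion urine condition. VGPR has two routes: detectable by immunofixation only, or a fall of at least 90% with low urine M-protein. CR and sCR are absolute states. Every category needs two consecutive assessments.

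Section 7.1.8.1 tests the response rates against a historical control with an exact binomial test. It does not give the control rate.

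**The concern.** Of two untreated readings, the later one best describes the patient at the start of treatment. The plan uses it only when it is the higher. If M-protein rises before dosing, the baseline moves up to Cycle 1 Day 1. If it falls, the baseline stays at the older screening value, and the fall is counted as response to pembrolizumab, lenalidomide and dexamethasone. Because the choice runs in one direction, the effect cannot average out across patients.

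The first baseline, before ASCT, already mixes in the effect of the transplant. The second is therefore the only response baseline aimed at the study regimen. It feeds a p-value against a historical control, and the responders it defines also form the DOR analysis set and the groups in the exploratory biomarker comparisons.

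**Working it through.** **The plan's own figure.** The only design calculation is for 12-month PFS (7.1.3). It reproduces: the early termination probability is P(X ≤ 8) for X ~ Bin(15, 0.5) = 0.696, and the expected size is 15 + 28 × (1 − 0.696) = 23.5. There is no such calculation for the response rates, and this one does not bear on the point.

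**Direction.** Let S be the screening value and C the Cycle 1 Day 1 value. The baseline is B = max(S, C) ≥ C. PR requires an on-study value of at most 0.5 × B. A higher B can only make this easier than with C, so no patient who responds against C is lost. When C ≥ S, the rule and a Cycle 1 Day 1 baseline coincide.

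**Thresholds.** Suppose M-protein falls by a fraction d from screening to Cycle 1 Day 1, so that C = (1 − d) × S and B = S. The further fall from C that is needed is 1 − 0.5/(1 − d) for PR and 1 − 0.1/(1 − d) for the 90% route to VGPR. The values of d are assumptions.

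| Pre-dose fall d | Further fall for PR | Further fall for VGPR, 90% route |
|---|---|---|
| 0% | 50% | 90% |
| 20% | 37.5% | 87.5% |
| 30% | 28.6% | 85.7% |
| 50% | 0% | 80% |

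CR, sCR and the immunofixation route to VGPR contain no percentage fall from baseline, so they do not change.

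**False PR with no drug effect.** A simulation of 400,000 patients per setting used readings on days −28, 0, 21, 42, 63 and 84 with log-normal error. PR was a fall of at least 50% at two consecutive on-treatment visits. The error CV and the decline rates are assumptions, and 28 days is the longest gap allowed.

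| Setting | Higher-value rule | Cycle 1 Day 1 |
|---|---|---|
| Stable disease, CV 10% | 0.00% | 0.00% |
| Stable disease, CV 20% | about 0.4% | about 0.2% |
| Stable disease, CV 30% | about 4.7% | about 2.5% |
| 37% fall ending by Day 1, CV 10% | 2.7% | 0% |
| 43% fall ending by Day 1, CV 10% | 12.5% | 0% |
| 50% fall ending by Day 1, CV 10% | 50% | 0% |
| Continuing decline, half-life 120 days, CV 10% | about 9% | 0.4% |
| Continuing decline, half-life 90 days, CV 10% | 51% | 5% |
| Continuing decline, half-life 70 days, CV 10% | 93% | 30% |

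The 90-day row shows the mechanism. Without error, the fall from screening is 1 − 0.5^(91/90) = 50.4% on day 63 and 1 − 0.5^(112/90) = 57.8% on day 84, which is a confirmed PR. From Cycle 1 Day 1 the falls are 1 − 0.5^(63/90) = 38.4% and 1 − 0.5^(84/90) = 47.6%, which is not.

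**Effect on the test.** Assume n = 43 and a control rate of 30%. The exact one-sided 5% test rejects at 19 or more responders, with type I error 0.034. If the rule adds 2 points to ORR, this becomes 0.063; if it adds 5 points, 0.136. The 2 and 5 points are illustrations, not estimates.

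**The case against.** The strongest reply is that the effect is small, of unknown size, and confined to secondary endpoints. The go/no-go decision rests on 12-month PFS. A second response baseline is prespecified. Measurable disease is required only at diagnosis, so some patients may have no measurable M-protein after ASCT and are not judged by a percentage fall in it. The 28-day gap is a maximum. No document gives the M-protein trend 60 to 180 days after transplant. A Cycle 1 Day 1 baseline also leaves in place any decline that continues during treatment: with a 70-day half-life, 30% false PR remains. All of this stands. It limits how much the point matters, but gives no reason to prefer the higher value.

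Three stronger readings are tempting and should not be drawn:

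- **Noise is counted as response.** The larger of two readings exceeds their mean by 0.564 SD on average, so at a CV of 10% the baseline is about 5.6% too high. That alone does not produce a PR: two consecutive falls of at least 50% are required, and the simulated rate at that CV is zero under either rule.
- **Both response rates are inflated alike.** For CR + sCR + VGPR only the 90% route moves, and only slightly.
- **The rule lengthens PFS or TTP.** Table 6 in Appendix 11.5 does use "Increase of ≥25% from baseline in Serum M-component", but section 7.1.6.1 attaches the higher-value rule to the response rates only. Nor can one apply the percentage alone, as in 1.25/0.8 − 1 = 56%: the criterion also needs an absolute rise of 0.5 g/dL, which governs whenever the baseline is below 0.5/0.25 = 2 g/dL. Some progression criteria, such as new bone lesions, do not use the M-protein baseline at all.

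**Conclusion.** The point holds for the secondary response endpoints, and mainly for PR within ORR. The direction follows from the documents alone: both readings are planned before the first dose, no myeloma therapy is allowed after ASCT, and the higher value can only add responders. The size does not follow from them. An assumed pre-dose fall of 20% lowers the further fall needed for PR to 37.5%, but such a fall creates almost no responders on its own if it stops by Day 1. Material numbers of false PRs need either a pre-dose fall approaching 50% or a decline that continues into treatment. The false-PR rates and type I error figures above rest on assumed trends, error and control rate.

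The CR and sCR rates are untouched, and the documents give no basis for extending the point to the primary endpoint. This is a minor but worthwhile correction.

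**What to change.** In section 7.1.6.1, under both response bullets, define the on-study baseline as the last value taken before the first dose: Cycle 1 Day 1, or screening only if the Cycle 1 Day 1 value is missing. Tie the wording to the first dose rather than to the visit label, because footnote 13 of the flow chart allows disease assessments within 7 days either side of Day 1. Keep the higher-value rule, if wanted, as a sensitivity analysis only.

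The cost is one line of text in each bullet. Both readings are already scheduled, so no visit, sample or patient is added. The reported ORR may be slightly lower. The change removes only the pre-dose part of any continuing post-ASCT decline; the report should say that the remainder cannot be separated from drug effect in a single-arm trial.
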